8.2.4 Prior and Concomitant Medications

Medications taken during this study will be coded using the World Health Organization Drug Dictionary Enhanced (WHO-DDE) and categorized as the following:

- **Prior medication:** any medication that started before the first dose of study drug, regardless of when the medication ended.
- **Concomitant medication:** medication continued or newly received at or after the first dose of study drug through the end of TE period.
- **Post-treatment medication:** medication continued or newly received after the TE period.

A given medication can be classified as a prior, a concomitant, or a post-treatment medication; both prior and concomitant; both concomitant and post-treatment; or prior, concomitant, and post-treatment. If a medication has a missing or partially missing start/end date and it cannot be determined whether it was taken before the first dose, concomitantly, or beyond the TE period, it will be considered as prior, concomitant, and post-treatment.

For the FAS, prior medications and concomitant medications will be summarized descriptively by: 1) preferred name; and 2) anatomic class (ATC) level 1, ATC level 2, and preferred name. Frequent ($\geq 5\%$ in any treatment group) prior medications and concomitant medications will be summarized descriptively by preferred name. Post-treatment medications will be listed by subject.

As an intermediate step for programming purposes, medications with missing or partially missing start dates will use 2000 to impute a missing year, January for a missing month, and 1 for a missing day. Medications with missing or partially missing stop dates will use 2050 to impute for a missing year, December for a missing month, and the last day of the month for a missing day. The logic to decide the category of a medication is presented in Table 8-1:

Table 8-1 Logic for Determining the Category of a Medication

Medication start date	Medication end date		
	< first dose date of study drug	\geq first dose date and \leq End date of TE period	> End date of TE period
< first dose date of study drug	P	PC	PCA
\geq first dose date and \leq End date of TE period	-	C	CA
> End date of TE period	-	-	A

P: Prior; C: Concomitant; A: Post

8.2.5 Study Drug Exposure

Exposure summaries will be based on the FAS.

Duration of study drug exposure is defined as follows: last dose date – first dose date + 1 day, regardless of any interruption in dosing between the first and the last dose.

Duration of study drug exposure expressed in weeks will be summarized descriptively (number, mean, SD, median, minimum, and maximum) and also into the following categories: ≤ 2 weeks, $>2 - \leq 4$ weeks, $>4 - \leq 8$ weeks, $>8 - \leq 16$ weeks, and $>16 - \leq 24$ weeks, >24 weeks. Additionally, the total duration of study drug exposure, defined as the sum of the subject's duration of treatment exposure and expressed in patient years, will be provided.

8.2.6 Study Drug Compliance

Study drug compliance will be measured by the compliance rate and be summarized based on the FAS.

Compliance rate will be calculated as follows:

$$100 \times [1 - (\text{Total number of days study drug interrupted}) / (\text{Duration of study drug exposure})].$$

The total number of days of study drug interrupted is defined as the sum of (number of unique days of study drug interrupted in each interruption interval), where number of days of study drug interrupted in each interval is defined as the interruption end date - the corresponding interruption start date + 1.

The Compliance rate will be summarized descriptively by the number of subjects (n), mean, SD, median, min, and max and into the categories of <80% or ≥80%.

A list of subjects with <80% of compliance rate will be provided.

8.2.7 Important Protocol Deviations

Important protocol deviations (IPD) are a subset of protocol deviations that may significantly impact the completeness, accuracy, and/or reliability of the study data or that may significantly affect a subject's rights, safety, or well-being. IPDs rules will be developed and finalized before database lock.

The protocol deviations that should be considered as potential IPDs include, but are not limited to:

- Subject entered the study despite violation of any inclusion or exclusion criteria
- Subject was less than 80% compliant with study medications
- Subject received excluded concomitant medications
- Subject received the wrong treatment or incorrect doses
- Subject remained in study despite meeting withdrawal criteria

Occurrence of any of these events should be considered as potential IPDs, but the blinded team should categorize them as IPDs only if they have the potential to affect interpretation of study results.

IPDs (from the clinical database or from the site deviation log) will be summarized descriptively based on the FAS and presented by treatment. Additionally, IPDs will be provided as a subject data listing.

8.3 Efficacy Analysis

Unless otherwise defined, all efficacy analyses described in this section will be based on the FAS. The FAS will be used in the summary of demographics and baseline characteristics and analyses of the efficacy data; subjects will be analyzed according to their randomized treatment assignment.

8.3.1 Primary Efficacy Endpoint

8.3.1.1 Definition of Primary Efficacy Endpoint

The primary efficacy endpoint is the absolute change from baseline in percent predicted FEV₁ (with a unit of percentage points) through Week 24.

Percent predicted FEV₁ is the ratio of FEV₁ (L) to the predicted FEV₁ (L), expressed as a percentage. The predicted FEV₁ will be calculated using the Hankinson¹ and Wang² standards; details are in Section 11.3.

8.3.1.2 Primary Analysis of Primary Efficacy Endpoint

The primary analysis will be based on a mixed model for repeated measures (MMRM) implemented using SAS PROC MIXED with a REPEATED statement. The null hypothesis to be tested is that the mean absolute change from baseline in percent predicted FEV₁ through Week 24 is the same for TEZ/IVA and placebo. A *P* value of 0.05 or less will be interpreted as sufficient evidence to reject the null hypothesis.

The model includes absolute change from baseline in percent predicted FEV₁ at each post-baseline visit (Day 15, and Weeks 4, 8, 12, 16, and 24) as the dependent variables, and the following fixed effects: treatment, visit, treatment-by-visit interaction, sex, age group (<18 versus ≥18 years old) at Screening, baseline percent predicted FEV₁, and baseline percent predicted FEV₁-by-visit interaction. An unstructured covariance structure will be used to model the within-subject errors. If the analysis fails to converge, a compound symmetry covariance structure will be used. Denominator degrees of freedom for the *F*-test for fixed effects will be estimated using the Kenward-Roger approximation³.

The LS Mean (SE) of the overall treatment difference between TEZ/IVA and placebo in absolute change from baseline in percent predicted FEV₁ from Day 15 through Week 24 will be presented along with the 95% confidence interval and a 2-sided *P* value.

Absolute change from baseline in percent predicted FEV₁ at each visit

The LS Mean (SE) of within-treatment group change from baseline at each post-baseline visit along with the 95% CI will be estimated from the above MMRM model. The LS Mean (SE) of the treatment difference between TEZ/IVA and placebo at each post-baseline visit will be provided along with the corresponding 95% CI and p-value. The LS means (with 95% CI) at each visit will also be plotted by treatment group. In addition, the post-baseline raw values and the absolute change from baseline in percent predicted FEV₁ at each post-baseline visit will be summarized descriptively (n, mean, SD, median, minimum, and maximum). The cumulative distribution of the absolute change from study baseline in ppFEV₁ through week 24 will be plotted by treatment group.

[REDACTED]

[REDACTED]

[REDACTED]

8.3.2 Secondary Efficacy Endpoints

The following are the key secondary efficacy endpoints:

- Relative change from baseline in percent predicted FEV₁ through Week 24
- Number of pulmonary exacerbations through Week 24
- Absolute change from baseline in BMI at Week 24
- Absolute change from baseline in CFQ-R respiratory domain through Week 24

The study also has the following other secondary efficacy endpoints:

- Time-to-first pulmonary exacerbation through Week 24
- Absolute change in sweat chloride from baseline through Week 24
- Absolute change in BMI z-score from baseline at Week 24 (in subjects <20 years of age at time of screening)
- Absolute change in body weight from baseline at Week 24

8.3.2.1 Definition of Secondary Efficacy Endpoints

8.3.2.1.1 Key Secondary Efficacy Endpoints

Relative change in percent predicted FEV₁ from baseline through Week 24

The calculations of percent predicted FEV₁ and the relative change from baseline at each post baseline visit will follow the definitions in Section 8.3.1.1 and Section 8.1.

Number of pulmonary exacerbations through Week 24

The pulmonary exacerbation (PEX) analysis period will start from the first dose of study drug and end on the last efficacy assessment up to Week 24.

Pulmonary exacerbation: A pulmonary exacerbation is defined as a new event or change in antibiotic therapy (IV, inhaled, or oral) for any 4 or more of the following signs/symptoms:

- Change in sputum
- New or increased hemoptysis

- Increased cough
- Increased dyspnea
- Malaise, fatigue, or lethargy
- Temperature above 38°C (equivalent to approximately 100.4°F)
- Anorexia or weight loss
- Sinus pain or tenderness
- Change in sinus discharge
- Change in physical examination (PE) of the chest
- Decrease in pulmonary function by 10%
- Radiographic changes indicative of pulmonary infection

The number of pulmonary exacerbations through Week 24 will be analyzed by comparing the *annualized number of pulmonary exacerbations* for each treatment group. It will be calculated as

$$48 \times (\text{total number of pulmonary exacerbations}) / (\text{total duration of post-baseline assessment in weeks}),$$

where total number of pulmonary exacerbations and total duration of post-baseline assessment are obtained from all subjects in the same treatment group.

Absolute change from baseline in BMI at Week 24

To calculate absolute change from baseline in BMI at Week 24, BMI will be calculated as:

$$\text{BMI} = \text{Weight (kg)} / (\text{height [m}^2\text{)})$$

Absolute change from baseline in CFQ-R respiratory domain through Week 24

The absolute change from baseline in the respiratory domain of the CFQ-R (Pooled 'Children Ages 12 and 13' Version and 'Adolescents and Adults' Version) through Week 24 will be analyzed based on the *CFQ-R scaled scores*, as elaborated below.

The CFQ-R^{5,6,7} is a valid CF-specific instrument that measures quality-of-life domains. This study uses three different versions of CFQ-R forms in this study:

- CFQ-R for Children Ages 12 and 13 has a total of 35 questions to form 8 domains. All questions are scored 1, 2, 3, or 4.
- CFQ-R for Adolescents and Adult (subjects 14 years and older) has a total of 50 questions to form 12 domains. Question 43, which is scored 1, 2, 3, 4, or 5, is not used in calculating any domain; all the other 49 questions are scored 1, 2, 3, or 4.
- CFQ-R for Parents/Caregivers (subjects 13 years and younger) has a total of 44 questions to form 11 domains. Question 37, which is scored 1, 2, 3, 4, or 5, is not used in calculating any domains; all the other 43 questions are scored 1, 2, 3, or 4.

For all three CFQ-R versions, to calculate the score for each domain, the response scores on the negatively phrased questions are reversed (reversed scores = 5 – response scores) so that 1 always represents the worst condition and 4 always represents the best condition.

The scaled score for each domain ranges from 0 (worst condition) to 100 (best condition). It is calculated as follows:

$$\text{Scaled score for a domain} = 100 \times (\text{mean}(\text{scores of all questions in that domain}) - 1)/3$$

The scaled score for a specific domain will not be calculated if more than half of the questions in the domain have missing scores.

Table 8-2, Table 8-3, and [Table 8-4](#) provide the questions included in each domain, the questions with the reversed scores, as well as the maximum number of missing questions for the CFQ-R for Children Ages 12 and 13, the CFQ-R for Adolescents and Adults, and the CFQ-R for Parents/Caregivers respectively. The CFQ-R scoring manual is also provided in [Section 11.4](#).

Table 8-2 CFQ-R for Children Ages 12 and 13

Domain	Questions			Maximum number of missing questions
	Total	Individual	Reversed questions	
Physical	6	1, 2, 3, 4, 5, 6	1, 2, 3, 4, 5	3
Emotion	8	7, 8, 9, 10, 11, 12, 13, 14	14	4
Social	7	20, 21, 22, 23, 24, 25, 26	20, 22, 24, 26	3
Body	3	27, 28, 29	-	1
Eat	3	15, 17, 19	19	1
Treatment burden	3	16, 18, 30	18	1
Respiration	4	31, 32, 33, 34	-	2
Digestion	1	35	-	0

Table 8-3 CFQ-R for Adolescents and Adults (Subjects 14 Years and Older)

Domain	Questions			Maximum number of missing questions
	Total	Individual	Reversed questions	
Physical	8	1, 2, 3, 4, 5, 13, 19, 20	13	4
Role	4	35, 36, 37, 38	35	2
Vitality	4	6, 9, 10, 11	6, 10	2
Emotion	5	7, 8, 12, 31, 33	-	2
Social	6	22, 23, 27, 28, 29, 30	23, 28, 30	3
Body	3	24, 25, 26	-	1
Eat	3	14, 21, 50	-	1
Treatment burden	3	15, 16, 17	15, 17	1
Health perceptions	3	18, 32, 34	18, 32, 34	1

Table 8-3 CFQ-R for Adolescents and Adults (Subjects 14 Years and Older)

Domain	Questions		Reversed questions	Maximum number of missing questions
	Total	Individual		
Weight	1	39	-	0
Respiration*	6	40, 41, 42, 44, 45, 46	43	3
Digestion	3	47, 48, 49	-	1

*: Question 43 not used to calculate a domain.

Table 8-4 CFQ-R for Parents/Caregivers (Subjects 13 Years and Younger)

Domain	Questions		Reversed questions	Maximum number of missing questions
	Total	Individual		
Physical	9	1, 2, 3, 4, 5, 13, 14, 15, 16	15	4
Vitality	5	8, 9, 10, 11, 12	10, 12	2
Emotion	5	6, 7, 23, 25, 26	6	2
School	3	27, 28, 29	28	1
Body	3	19, 20, 21	-	1
Eat	2	17, 44	-	0
Treatment burden	3	18, 30, 31	31	1
Health perceptions	3	22, 24, 32	22, 24, 32	1
Weight	1	33	-	0
Respiration*	6	34, 35, 36, 38, 39, 40	37	3
Digestion	3	41, 42, 43	-	1

*: Question 37 not used to calculate a domain.

8.3.2.1.2 Other Secondary Efficacy Endpoints

Time to First Pulmonary Exacerbation through Week 24

The *time to first pulmonary exacerbation* is defined as the number of days from the first dose of study drug to the date of the first pulmonary exacerbation.

Absolute change in sweat chloride from baseline through Week 24

Sweat chloride will be collected at baseline and 3 post-baseline time points (Weeks 4, 16, and 24). Values > 160 mmol/L or < 10 mmol/L will be set to missing.

Absolute change from baseline in sweat chloride will be calculated as, $mean(SW_{Left}, SW_{Right}) - SW_{Base}$, where SW_{Left} and SW_{Right} are the measurements obtained on the left and right arms, respectively, at a particular visit and SW_{base} is the mean of right and left baseline measurements. If one of the two measurements at a time point is missing, the other will be used as the mean.

Note: A volume of ≥ 15 μL is required for an accurate determination of sweat chloride. Any results reported as having volume < 15 μL or “Quantity Not Sufficient” (QNS) will be considered missing.

Definition of Baseline: If sweat chloride collection was initiated for one arm prior to first dose and initiated for the other arm after the first dose, the baseline will consist of the single pre-dose measurement. If both sweat collections were initiated after the first dose, the baseline sweat chloride result will be considered missing for analysis purposes.

Absolute change from baseline in BMI z-score at Week 24 for subjects <20 years old at screening

BMI will be calculated from weight and height at baseline and at the 6 post-baseline time points (Day 15, Week 4, 8, 12, 16, and 24).

BMI, adjusted for age and sex, will be referred to as BMI-for-age z-score (BMI z-score). BMI z-score will be calculated by using Centers for Disease Control and Prevention (CDC) growth charts⁸. The BMI z-score will be calculated as follows:

$$z = \begin{cases} \frac{\left(\frac{X}{M}\right)^L - 1}{LS}, & L \neq 0 \\ \frac{\ln\left(\frac{X}{M}\right)}{S}, & L = 0 \end{cases}$$

where X is the derived BMI value in kg/m^2 based on the raw weight and raw height and L , M , and S are selected from the CDC BMI-for-age chart by subject sex and age. The BMIAGE file contains these parameters by sex (1=male, 2=female) and age; it is available at: http://www.cdc.gov/growthcharts/percentile_data_files.htm. SAS code for calculating percentiles and z-scores is available at: http://www.cdc.gov/growthcharts/computer_programs.htm.

NOTE: The CDC BMI-for-age charts are designed for use in pediatric populations (2 to 20 years of age); in this analysis plan, BMI z-score will be calculated only for subjects between 2 and <20 years of age at screening.

Absolute change from baseline in body weight at Week 24

Weight will be collected at baseline and at 6 post-baseline time points (Day 15, Week 4, 8, 12, 16, and 24) according to the Schedule of Assessments (see Section 11.1). The absolute change from baseline in body weight will be calculated at each post-baseline visit following the general definition of the change from baseline in Section 8.1.

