11.6.2 Sweat Chloride Testing

The sweat chloride test is a standard diagnostic tool for CF, serving as a biomarker of CFTR activity. Collection of sweat samples will be performed at visits specified in Table 3-1 and Table 3-2, using an approved collection device. Sweat samples will be sent to a central laboratory for testing and interpretation of results. Individual sweat chloride test results will not be disclosed to the study sites. Specific instructions for collection, handling, processing, and shipping of sweat chloride samples to the central laboratory will be provided separately.

The sweat chloride collection on Day 1, Week 4, Week 16, and Week 24 will occur approximately 1 hour before the PK sample collection and before the morning dose of the study drugs. At each time point, 2 samples will be collected, 1 from each arm (left and right). Additionally, sweat collection will be performed at the Screening Visit and ETT Visit. Collection of sweat chloride will not overlap with any other study assessments.

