12.3.1 General Considerations

All individual subject data for all randomized subjects exposed to study drug will be presented in data listings.

Continuous variables will be summarized using the following descriptive summary statistics: the number of subjects (n), mean, SD, median, minimum value (min), and maximum value (max). The precision of the measurement for each continuous variable will be specified in the SAP.

Categorical variables will be summarized using counts and percentages. Percentages will be presented to 1 decimal place.

Baseline value, unless otherwise specified, will be defined as the most recent non-missing measurement (scheduled or unscheduled) collected before the initial administration of study drug. For ECG, the baseline will be defined as the average of the 3 pretreatment measurements on Day 1.

Change (absolute change) from baseline will be calculated as post-baseline value - baseline value.

Relative change from baseline will be calculated as (post-baseline value - baseline value)/baseline value.

The treatment-emergent (TE) period will include the time from the first dose to the Safety Follow-up Visit or 28 days after the last dose of the study medication for subjects who do not have a Safety Follow-up Visit.

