8 STATISTICAL ANALYSIS

8.1 General Considerations

All individual subject data in the All Subject Set will be presented in data listings. The Schedule of Assessments is provided in Section 11.1. The precision standards are provided in Section 11.6.

Continuous variables will be summarized using the following descriptive summary statistics: the number of subjects (n), mean, standard deviation (SD), median, minimum value (min), and maximum value (max).

Categorical variables will be summarized using counts and percentages.

Baseline Value, unless otherwise specified, is defined as the most recent non-missing measurement (scheduled or unscheduled) collected prior to or on the first dose of study drug. For ECGs, the baseline will be defined as the average of the 3 pre-treatment measurements (triplicate) on Day 1. For sweat chloride, the baseline value will be the mean of last assessment values on the left and the right arm prior to the first dose of the study drug.

Change (Absolute Change) from baseline will be calculated as Post-baseline value – Baseline value.

Relative change from baseline will be calculated and expressed in percentage as $100 \times (\text{Post-baseline value} - \text{Baseline value}) / \text{Baseline value}$.

Treatment Emergent (TE) Period will include the time from the first dose of study drug to the Safety Follow-up Visit, or to 28 days after the last dose of the study drug for subjects who do not have a Safety Follow-up Visit, or to the last participation date in the study (i.e., the day right before the first study dose in the extension study for subjects who enrolled into the extension study), whichever occurs first. The TE period will be used for safety analyses unless otherwise specified.

Unscheduled Visits: Unscheduled visit measurements will be included in the following:

1. derivations of measurements at scheduled visits per specified visit windowing rules below;
2. derivations of baseline/last on-treatment measurements;
3. derivations of the maximum/minimum on-treatment values and maximum/minimum changes from baseline values for safety analyses;
4. data listings where appropriate.

Visit Windowing Rules: Section 11.2 defines the windows for protocol-defined visits. The windows will be applied using the following rules for both scheduled and unscheduled visits:

1. If no measurement is available within a visit window, the assessment will be considered missing for the visit;

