8.3.2.2.3 Analysis of Other Secondary Efficacy Endpoints

Time to first pulmonary exacerbation through Week 24

Analyses for the time to first pulmonary exacerbation through Week 24 will be based on a Cox regression model that will include treatment, sex, age group at screening (<18 vs. ≥18 years old), and baseline ppFEV₁ as covariates. In addition, the Kaplan-Meier (KM) method

will be used to estimate the cumulative exacerbation-free rate; the associated plot will be provided.

Subjects without any protocol-defined pulmonary exacerbation event by or prior to Week 24 will be considered censored at the date of the last visit (up to Week 24).

Note: If in either treatment group fewer than 5 subjects have pulmonary exacerbations, the Cox regression will not be performed and analysis of time-to-first event will be restricted to the Kaplan-Meier estimates.

Absolute change in sweat chloride from baseline through Week 24

Analysis of this variable will be performed using a model analogous to that used for the primary endpoint, with baseline ppFEV₁ replaced by baseline sweat chloride value, and baseline ppFEV₁-by-visit interaction replaced by baseline sweat chloride value-by-visit interaction. The LS Mean (SE) of the overall treatment difference between TEZ/IVA and placebo in absolute change from baseline in sweat chloride from Day 15 through Week 24 will be presented along with the 95% confidence interval and a 2-sided *P* value.

The LS Mean (SE) of within-treatment group absolute change from baseline at each post-baseline visit along with the corresponding 95% CI and p-value will be estimated from the same MMRM model. The LS Mean (SE) of the treatment difference between TEZ/IVA and placebo at each post-baseline visit also will be provided along with the corresponding 95% CI and p-value. The LS means (with 95% CI) at each post-baseline visit also will be plotted by treatment group. Summary statistics for the raw values and the absolute change from baseline in sweat chloride at each visit will be presented.

Absolute change in BMI z-score from baseline at Week 24 for subjects <20 years old at screening

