11.2 Analysis Visit Window Mapping Rules for Efficacy and Safety Measurements

Table 11-3 Visit Window Mapping Rules

Assessments	Visit	Target Study Day	Visit Window (in study days)

 • Weight and height • Vital signs • Pulse oximetry • Labs 
 ○ Chemistry ○ Hematology 	Baseline	1	[screening visit, pre-dose Day 1]
	Day 15	15	[1*, 22]
	Week 4	29	[23,43]
	Week 8	57	[44, 71]
	Week 12	85	[72, 99]
	Week 16	113	[100, 141]
	Week 24	169	[142, 183]
	ETT	N/A	Follow the individual visit window to be mapped to individual visits
	Safety Follow-up Visit (SFU)	N/A	Efficacy assessments: follow the individual visit window to be mapped to individual visits if measured before / on Day 183 or remain as SFU if otherwise. Safety assessments: remain as SFU.

 • Spirometry • Standard 12-lead ECG 	Baseline	1	[screening visit, pre-dose Day 1]
	Day 1 Predose and Postdose (Spirometry, or ECG)	1	Nominal
	Day 15 Predose and Postdose (Spirometry, or ECG)	15	Nominal
	Day 15 Spirometry, or ECG	15	[2,15] if no nominal Day 15
	Week 4 (Spirometry, or ECG)	29	[Nominal Day 15+1, 43] if there is nominal Day 15; [16, 43] otherwise.
	Week 8	57	[44, 71]
	Week 12	85	[72, 99]
	Week 16	113	[100, 141]

	Week 24	169	[142, 183]
	ETT	N/A	Follow the individual visit window to be mapped to individual visits
	Safety Follow-up Visit (SFU)	N/A	Efficacy assessments: follow the individual visit window to be mapped to individual visits if measured before / on Day 183 or remain as SFU if otherwise. Safety assessments: remain as SFU.
• CFQ-R	Baseline	1	[screening visit, Day 1]
	Week 4	29	[2, 43]
	Week 8	57	[44, 71]
	Week 12	85	[72, 99]
	Week 16	113	[100, 141]
	Week 24	169	[142, 183]
	ETT	N/A	Follow the individual visit window to be mapped to individual visits
• Sweat chloride	Baseline	1	[screening visit, pre-dose Day 1]
	Week 4	29	[1*, 71]
	Week 16	113	[72, 141]
	Week 24	169	[142, 183]
	ETT	N/A	Follow the individual visit window to be mapped to individual visits
• Vitamin levels • Lipid panel	Baseline	1	[screening visit, pre-dose Day 1]
	Week 12	85	[1*, 127]
	Week 24	169	[128, 183]

 • Complete PE • [REDACTED] • Labs 
 ○ Coagulation ○ Urinalysis 	Baseline	1	[screening visit, pre-dose Day 1]
	Week 24	169	[1*, 183]
	Safety Follow-up Visit (no Complete PE, [REDACTED])	N/A	Nominal

1* only include day 1 post-dose measurements.

Note:

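### The sweat chloride baseline paragraph in SAP 8.3.2.1.2, read naturally as about the Day 1 pair, conflicts with the baseline rule in SAP 8.1 and the window table in SAP 11.2

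*SAP*

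**What the plan says.** Three places in the SAP bear on the sweat chloride baseline.

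- **SAP 8.1 (General Considerations)** has a sentence specific to sweat chloride: "the baseline value will be the mean of last assessment values on the left and the right arm prior to the first dose". It is not limited to Day 1.
- **SAP 11.2 (window table)** gives the sweat chloride baseline window as "screening visit, pre-dose Day 1", so a Screening value qualifies.
- **SAP 8.3.2.1.2 (Definition of Baseline paragraph)** has two rules. If one arm was collected before the first dose and the other after, "the baseline will consist of the single pre-dose measurement". For two late arms it says: "If both sweat collections were initiated after the first dose, the baseline sweat chloride result will be considered missing for analysis purposes".

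Protocol 12.3.1 gives the general definition as the "most recent non-missing measurement (scheduled or unscheduled) collected before the initial administration of study drug". Protocol 11.6.2 schedules the Screening collection: "Additionally, sweat collection will be performed at the Screening Visit and ETT Visit". Protocol Table 3-1 and SAP Table 11-1 mark it for all subjects without condition.

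**The concern.** Two programmers working from different sections of the same SAP could derive different baselines for the same subject. In the two-late-arms case one would have a number and the other would have none.

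The difference matters because baseline is used twice. It is part of the change score, and SAP 8.3.2.2.3 also puts it in the mixed model for repeated measures (MMRM), where baseline percent predicted FEV1 is "replaced by baseline sweat chloride value" and its by-visit interaction is replaced likewise. SAP 8.1 does not impute missing data unless otherwise specified, and nothing is specified for this baseline. A subject whose baseline is set to missing therefore loses the Week 4, 16 and 24 values from the analysis, even where a usable pre-dose result is on file.

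The missing-baseline rule also treats similar subjects differently. A subject whose Day 1 samples were never taken, or were too small in volume, keeps the Screening baseline under SAP 8.1 and 11.2. A subject whose Day 1 samples were taken late loses it, although a late sample does nothing to invalidate an earlier one.

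**Working it through.** The plan states no figure on this point, so the check sets the rules side by side and applies them to two cases. The mmol/L values are invented for illustration.

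**Case A: both Day 1 arms collected after the first dose.** Screening left 100, right 104.
- SAP 8.1 and 11.2: last pre-dose value on each arm, (100 + 104)/2 = 102.
- SAP 8.3.2.1.2: missing.

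**Case B: Day 1 left arm before the dose, right arm after.** Screening left 100, right 104; Day 1 left 98.
- SAP 8.1, taken arm by arm: (98 + 104)/2 = 101.
- SAP 8.3.2.1.2: 98.

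Both cases assume two arms were sampled at Screening. Protocol 11.6.2 asks for one sample from each arm at each time point, but that sentence comes directly after the Day 1 to Week 24 schedule and just before the Screening sentence. If only one arm was sampled at Screening, Case A still diverges (one value against missing). Case B then diverges only if that arm was the one collected late on Day 1.

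**Does any text rank the rules?** The words in SAP 8.1 that allow for exceptions attach to its general baseline definition. The sweat chloride sentence is already such an exception, so SAP 8.3.2.1.2 is a second specific rule and not a clear override. SAP Section 3 ranks the SAP above the protocol, which does not settle a conflict inside the SAP.

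**How many subjects?** The documents give no rate of late Day 1 collection. With an assumed range of 0.5% to 2% and the planned 490 subjects:
- 490 × 0.005 = 2.45, about 2 subjects.
- 490 × 0.02 = 9.8, about 10 subjects.

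**Effect on precision.** Taking the standard error as proportional to 1/√n:
- 0.5% lost: 1/√0.995 = 1.0025, an increase of about 0.25%.
- 2% lost: 1/√0.98 = 1.010, an increase of about 1%.

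**Age of a Screening baseline.** The Screening Period is 28 days, and Protocol 8.1.1.3 allows a one-week extension: 28 + 7 = 35 days, or 5 weeks. Protocol 8.1.1.2 exempts sweat chloride from repetition at rescreening, so the value can be older in rescreened subjects.

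**The case against.** The best defence is that the disputed sentence never says Day 1. A Screening collection is by definition started before the first dose. The sentence could therefore mean only that, where no pre-dose collection exists at all, post-dose samples may not stand in. On that reading there is no conflict in the two-arm case. This reading is possible but strained. The sentence before it describes a left/right pair with one arm before and one after the first dose, which fits only a collection on the first dosing day. With Screening collection scheduled for everyone, the rule would also have almost nothing to act on. The ambiguity still means the contradiction should not be called certain.

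A second defence is that SAP 8.3.2.1.2 is the endpoint's own section and a programmer could reasonably let it govern. That is fair, but the SAP does not say so, and SAP 8.1 has its own sweat chloride sentence.

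Third, the SAP 8.1 sentence might be read by occasion and not arm by arm. The last pre-dose assessment in Case B would then be Day 1 with one arm, which agrees with SAP 8.3.2.1.2. The one-arm half of the conflict is thus less firm than the two-arm half.

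Fourth, insisting on a baseline taken close to the first dose is a defensible choice if it is made openly.

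A reader might go further and infer that valid data are always thrown away, or that the treatment comparison is biased. The documents support neither. A Screening result can itself be missing, below 15 µL or outside 10 to 160 mmol/L. In a double-blind trial, nothing links a late Day 1 collection to treatment arm.

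**Conclusion.** The point holds as an inconsistency to be reconciled, on the natural reading that the paragraph concerns the Day 1 pair. With both arms late, one SAP section gives a missing baseline while two other places give a Screening-based one. With one arm late, the sections also differ if SAP 8.1 is applied arm by arm.

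The practical effect is small. The protocol requires Day 1 collection before the morning dose, so each case is a departure from schedule. Sweat chloride change is an other secondary endpoint and does not appear in the SAP 8.3.2.2.2 hierarchy, so no primary or key secondary conclusion depends on it. The expected cost is slightly lower precision, about 1% on the standard error at the top of the assumed range. The counts of 2 to 10 subjects rest entirely on that assumed range and are not estimates from the trial.

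**What to change.** Rewrite the whole Definition of Baseline paragraph in SAP 8.3.2.1.2 so that it agrees with SAP 8.1 and 11.2. Changing only the two-late-arms sentence would leave the one-arm rule unreconciled. Suggested wording:

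*Baseline sweat chloride is the mean of the last valid pre-dose value on the left arm and the last valid pre-dose value on the right arm, with Screening values included. A value is valid if the sample volume is at least 15 µL and the result lies within 10 to 160 mmol/L. If only one arm has a valid pre-dose value, that value is used. Baseline is missing only if neither arm has one.*

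If the sponsor prefers the stricter rule, it should say in SAP 8.1 and 11.2 that SAP 8.3.2.1.2 governs, name Day 1 explicitly, and give the reason.

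The cost is one paragraph, to be settled before data lock and unblinding. The downside is that a few baselines will be up to about 5 weeks old, or older in rescreened subjects. In Case B the two arms would also come from different days.
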